## 9.6 Statistical Methods

The primary hypothesis is related to proportion of correct response in the OCL task associated with change from placebo run-in period (Week -1) at Week 8 for donepezil group compared with placebo group. To assess the primary hypothesis, the repeated measurements

associated with proportion of correct response in the OCL task at each of Weeks -1, 2, 4, 6 and 8 will be averaged by each participant. Intermittent missing repeated measures within a time point (e.g., Week 2) will not be imputed and data will be averaged as available. Observations with integrity failures will be excluded from analysis and will not be imputed. The amount and patterns of missing data will be summarized. Change from placebo run-in period in the average correct response of OCL measurements will be estimated using a linear mixed effects model containing fixed effects for Week, proportion of correct response in the OCL measurement at baseline (placebo run-in period), Treatment (donepezil/placebo) and Week by Treatment interaction with an unstructured covariance matrix which will account for missing data under a missing at random assumption. Least square variances will be estimated for change from placebo run-in period by treatment group (donepezil/placebo) and Week 8 using above mentioned linear mixed models. The posterior distribution of the variances will be estimated by generating 10,000 independent draws from non-informative Inverse Gamma prior for both treatment groups. Conditioned on each variance, difference of average correct response rate of OCL task from placebo run-in period will be generated from a Normal distribution with mean equal to the estimated least square mean estimate for both groups at Week 8. The posterior probability of true mean difference between donepezil and placebo group at Week 8 relative to Week -1 is greater than 2 percentage points will be derived from the posterior distribution. We can rewrite the model as following

$$\sigma^2 \sim \text{Inverse Gamma}(\alpha, \beta), \text{ where } \alpha = \beta = 0.0001$$
$$\sigma_{trt}^2 | y_{iw} \propto \text{Inverse Gamma} \left( \alpha + \frac{n_{trt}}{2}, \beta + \frac{n_{trt}}{2} S_{trt}^2 \right), \text{ where } trt = \text{donepezil, placebo}$$
$$y_i | \cdot \sim \text{Normal}(\hat{\mu}_{trt}, \sigma_{trt}^2 | \cdot), \text{ where } i = \begin{cases} 1, \dots, 24 & \text{when } trt = \text{donepezil} \\ 1, \dots, 12 & \text{when } trt = \text{placebo} \end{cases}$$

The above equations will be repeated for 10,000 times to estimate

$$\text{Prob} \left( (\bar{y}_{\text{donepezil}} - \bar{y}_{\text{placebo}}) > 0.02 \right)$$

A posterior probability that is > 55% will satisfy the primary hypothesis.

To assess the secondary hypothesis related to the true standard deviation (SD) associated with the change from placebo run-in period in average OCL measurements, the individual OCL measurements will first be transformed using the arcsine square root function. For each patient, the 3 transformed OCL measurements at each of Weeks -1, 2, 4, 6 and 8, will be averaged. Intermittent missing repeated measures within a time point (e.g., Week 2) will not be imputed and data will be averaged as available. The amount and patterns of missing data will be summarized. The variance/covariance matrix of the average transformed OCL measurements will be estimated using a linear mixed effects model containing fixed effects for Week, Treatment (donepezil/placebo) and Week by Treatment interaction. An unstructured covariance matrix will be estimated that principally accounts for missing data under missing at random assumption. The Kenward & Roger's approximation will be used to compute the appropriate model-based degrees of freedom. Utilizing a non-informative prior,

the posterior distribution of the true variance/covariance matrix will be estimated by generating 5000 independent draws from an inverse Wishart distribution, with the model based degrees of freedom and matrix S, where S is the model-based degrees of freedom times the model estimated variance/covariance matrix. For each generated true variance/covariance matrix, a plausible true SD of the change from baseline in average OCL measurements at Week 8 relative to Week -1 will be calculated. The posterior probability that the true SD of the change from baseline in average OCL measurements at Week 8 relative to Week -1 is  $\leq 0.1$  will be derived from the posterior distribution. A posterior probability that is  $> 70\%$  will satisfy the secondary hypothesis.

To assess the secondary hypothesis related to the effect of donepezil, least square variance will be estimated for change from placebo run-in period at Week 8 for donepezil group using above mentioned linear mixed models. The posterior distribution of the variance will be estimated by generating 10,000 independent draws from non-informative Inverse Gamma prior. That is, conditioned on variance, difference of average correct response rate of OCL task from placebo run-in period will be generated from a Normal distribution with mean equal to the estimated least square mean estimate for donepezil group at Week 8. The posterior probability that the true mean difference is greater than 2 percentage points will be summarized.

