### 9.1 Statistical Analysis Plan Summary

This section contains a brief summary of the statistical analyses for this study. Full detail is in the Statistical Methods (Section 9.6).

To assess the primary hypothesis, the repeated measurements associated with proportion of correct response in the OCL task at each of Weeks -1, 2, 4, 6 and 8 will be averaged by each participant. Intermittent missing repeated measures within a time point (e.g., Week 2) will not be imputed and data will be averaged as available. Observations with integrity failures will be excluded from analysis and will not be imputed. Change from placebo run-in period (i.e. Week -1) in the average correct response of OCL measurements will be estimated using a linear mixed effects model containing fixed effects for Week, proportion of correct response in the OCL measurement at baseline (placebo run-in period), Treatment (donepezil/placebo) and Week by Treatment interaction with an unstructured covariance matrix which will account for missing data under a missing at random assumption. Least square variances will be estimated for change from placebo run-in period by treatment group (donepezil/placebo) and Week 8 using above mentioned linear mixed models. The posterior distribution of the variances will be estimated by generating 10,000 independent draws from non-informative Inverse Gamma prior for both treatment groups. Conditioned on each variance, difference of average correct response rate of OCL task from placebo run-in period will be generated from a Normal distribution with mean equal to the estimated least square mean estimate for both groups at Week 8. The posterior probability of true mean difference between donepezil and placebo group at Week 8 relative to Week -1 is greater than 2 percentage points will be derived from the posterior distribution. A posterior probability that is > 55% will satisfy the primary hypothesis.

Power: The probability to satisfy the primary hypothesis under varying true mean change in donepezil population is shown in Table 9. With 36 participants (24 in donepezil and 12 in placebo), there is ~ 64% power to satisfy the criteria (posterior probability >55%) for the primary hypothesis if the true mean change from placebo run-in period is 3 percent points for donepezil group, assuming there no change in placebo group. For the donepezil group, if the true mean change is 4 percentage points then the corresponding power increases to 78%.

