## 9.5 Analysis Populations

The Full Analysis Set for each endpoint will be comprised of all participants who receive study medication and yield at least one valid measurement for that endpoint. Data from participants who discontinue donepezil therapy will be considered missing at time points after therapy discontinuation.

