## 9.9 Sample Size and Power Calculations

The probability to satisfy the primary hypothesis under varying true mean change in donepezil population is shown in [Table 10](#). There are 24 participants in the donepezil group and 12 participants in the placebo group. In the placebo group, true mean change from placebo run-in period is assumed to be zero with SD of 0.06. In the donepezil group, the SD of the change from placebo run-in is 0.07. SD in both groups are consistent with estimated SD from MK-0000-318 study. With 36 participants (24 in donepezil and 12 in placebo), there is  $\sim 64\%$  power to satisfy the primary hypothesis if the true mean change from placebo run-in period is 3 percentage points for donepezil group, assuming there no change in placebo group. For donepezil group, if the true mean change is 4 percentage points then the corresponding power increases to 78% as displayed in the last row of [Table 10](#).

Table 10 Power associated with Primary Hypothesis

| True Mean Change in Donepezil | Prob (Post prob. of difference of true mean change from placebo run-in between the donepezil and placebo groups > 0.02) > |         |         |
|-------------------------------|---|---------|---------|
|                               | P = 60%   | P = 55% | P = 50% |
| 2.0%                          | 0.407   | 0.456   | 0.509   |
| 2.5%                          | 0.483   | 0.532   | 0.582   |
| 3.0%                          | 0.576   | 0.635   | 0.684   |
| 3.5%                          | 0.669   | 0.713   | 0.754   |
| 4.0%                          | 0.741   | 0.778   | 0.816   |

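### Does Section 9.6 leave open which variance, per participant or of the mean, feeds the primary posterior probability?

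*Combined protocol and SAP*

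**What the plan says.** Section 9.6 first averages the One Card Learning repeats "at each of Weeks -1, 2, 4, 6 and 8 will be averaged by each participant". It then fits a mixed model to the change from run-in, with terms for week, baseline, treatment and week by treatment, "with an unstructured covariance matrix which will account for missing data under a missing at random assumption". From that model, "Least square variances will be estimated for change from placebo run-in period by treatment group (donepezil/placebo) and Week 8".

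The section then restates the procedure as equations:

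- σ²_trt, given the data y_iw (participant i, week w), is inverse gamma with parameters α + n_trt/2 and β + (n_trt/2)S²_trt, where α = β = 0.0001.
- y_i is drawn from a Normal distribution with the least-squares mean and σ²_trt, for i = 1 to 24 on donepezil and 1 to 12 on placebo.
- "The above equations will be repeated for 10,000 times to estimate" the probability that the difference between the two arm averages of y exceeds 0.02. Success requires more than 55%.

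The summary in Section 9.1 gives the draw step only in words: "Conditioned on each variance, difference of average correct response rate of OCL task from placebo run-in period will be generated from a Normal distribution". The donepezil-only secondary analysis at the end of Section 9.6 is also in words: "least square variance will be estimated for change from placebo run-in period at Week 8 for donepezil group". It has no equations of its own and no pass mark.

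For planning, Section 9.9 takes a placebo SD of 0.06 and says "In the donepezil group, the SD of the change from placebo run-in is 0.07". On losses, Section 9.5 states: "Data from participants who discontinue donepezil therapy will be considered missing at time points after therapy discontinuation".

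**The concern.** Neither S²_trt nor n_trt is defined in words. The model is described with one unstructured covariance matrix, so its Week 8 residual variance is common to both arms. The variance that differs by arm in ordinary output from such a model is that of the least-squares mean. A programmer could therefore take the squared standard error as S²_trt. The printed equations average 24 and 12 draws, so they already divide by n once, and a squared standard error would be divided by n again.

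The prose carries a second risk, because it does not mention averaging over participants. Read alone, it could mean one draw per arm with a per-participant variance, which would give far too wide a posterior.

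The posterior probability is the primary result. The donepezil-only posterior is reported without a threshold, so there the number is the whole finding. A lesser worry is that the index stays at 24 and 12 although Sections 6.6 and 9.5 can remove data.

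**Working it through.** **Inputs.** Section 9.9: SD 0.07 (donepezil, n = 24) and 0.06 (placebo, n = 12), with no change on placebo. Section 9.6: margin 0.02, bar 55%.

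**Reproducing Table 10.** With a per-participant S², averaged over n draws, the posterior SD is approximately the standard error of the difference:

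SE = √(0.07²/24 + 0.06²/12) = √(0.0002042 + 0.0003000) = 0.02245.

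The trial passes if the observed difference exceeds 0.02 + z × (posterior SD), with z = 0.1257 for the 55% bar. That is 0.02 + 0.1257 × 0.02245 = 0.0228. Power at a true 3 points is Φ((0.03 − 0.0228)/0.02245) = 0.625.

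**The misreading.** With a squared standard error in the same equations, the posterior SD becomes √(0.07²/24² + 0.06²/12²) = 0.00579, about 3.9 times too small. The pass mark falls to 0.0207.

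| True change, bar | Table 10 | Per-participant, averaged | Squared SE, averaged |
|---|---|---|---|
| 2 points, 55% | 0.456 | 0.450 | 0.487 |
| 3 points, 55% | 0.635 | 0.625 | 0.660 |
| 4 points, 55% | 0.778 | 0.778 | 0.805 |
| 3 points, 60% | 0.576 | 0.576 | 0.648 |

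On the per-participant reading all 15 cells agree within 0.02 (largest gap 0.684 against 0.672). With the squared standard error, all 10 cells in the 55% and 60% columns miss, by 0.024 to 0.080. The 50% column cannot discriminate, because z is zero there. One per-participant draw per arm gives posterior SD √(0.07² + 0.06²) = 0.0922 and power 0.472 at 3 points and the 55% bar, so it does not reproduce either.

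**What a misreading would cost.** Simulating the printed scheme, with 1,000,000 draws at an observed 3 points, gives a posterior of 0.665 as intended, 0.942 with a squared standard error, and 0.541 with one per-participant draw per arm. For donepezil alone the figures are 0.754, 0.999 and 0.557.

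**Pooled or by-arm variance.** If the single covariance matrix yields one common Week 8 variance, its planning value is (23 × 0.0049 + 11 × 0.0036)/34 = 0.00448. The posterior SD is then √(0.00448 × (1/24 + 1/12)) = 0.02366. At an observed 3 points the posterior is Φ(0.01/0.02366) = 0.664, against Φ(0.01/0.02245) = 0.672 by arm. Power at 3 points is 0.623 against 0.625. For donepezil alone the comparison is Φ(0.01/√(0.00448/24)) = 0.768 against Φ(0.01/√(0.0049/24)) = 0.758.

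**Fixed index.** The documents give no loss rate. Assuming 21 and 10 participants at Week 8, the standard error is √(0.0049/21 + 0.0036/10) = 0.02436. Keeping 24 and 12 makes the posterior SD 8% too small (0.02245/0.02436 = 0.922). Assuming 18 and 9, it is 13% too small (0.02245/0.02593 = 0.866). Simulated posteriors at an observed 3 points are 0.664 against 0.652, and 0.663 against 0.643.

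**The case for a change.** The best case for a change is that a reader should not have to work back from a power table to learn what enters the primary analysis. The model as described does not directly yield a variance for each arm, and the donepezil-only paragraph has no equations. Section 2.2 also wants these results as a benchmark for later compounds, where 0.67 and 0.94 would be read very differently.

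Part of this stands. S²_trt and n_trt are undefined in words, and a single covariance matrix sits awkwardly with a variance subscripted by arm.

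The rest does not carry. The large figures come from calculations that the plan does not specify: the printed update, the participant index and the arm averages leave room only for a per-participant variance, and they rule out a single draw per arm. The prose can be read the same way, since the repeats are first averaged within participant and the variance named is that of the change. The donepezil-only paragraph follows the same steps for one arm, so the same equations carry over naturally.

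The obvious remedy, a separate unstructured matrix for each arm, is also debatable. Four post-baseline weeks give 4 × 5/2 = 10 parameters, to be estimated from about 12 placebo participants. That risks non-convergence, and the choice between pooled and by-arm variance moves the posterior by only about 1 point.

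**Conclusion.** No change is needed. Followed as printed, the equations give a sound posterior and the power stated in Section 9.9. The missing definition is a gap that a competent analyst fills in the only way consistent with the equations and Table 10. Even the squared-standard-error mistake would raise the chance of passing by only about 2 to 4 points at true differences of 2 to 4 points. Its harm would be to the reported strength of evidence, and it would require departing from the printed scheme.

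The 24 and 12 are the planned sizes. n_trt is already a symbol in the variance line, and Sections 5.5 and 6.3.1 provide for replacement towards about 36 evaluable completers. Analysts would use the actual counts. If they did not, the posterior would shift by 1 to 2 points under the assumed losses.

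These figures rest on the Section 9.9 SDs, Normal changes and no baseline adjustment; the adjusted residual variance in the trial may differ. Except in the fixed-index comparison, they also assume no missing data.

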#### Hypotheses, Objectives, and Endpoints:

The following objectives will be evaluated in participants diagnosed with mild cognitive impairment or mild Alzheimer’s Disease.

| Primary Objectives   | Primary Endpoints  |
|--|--|
| 
- To assess the ability of a repeated high-frequency site-based computerized cognitive assessment to evaluate the potential treatment effects of donepezil compared with placebo in participants with MCI/mild AD following a limited treatment duration (8 weeks treatment).
 
Hypothesis: After 8 weeks of daily treatment, the change from the placebo run-in period (Week -1) in average proportion of correct responses on the One Card Learning (OCL) task (a task of visual learning) in participants receiving donepezil compared with participants receiving placebo will be <math>\geq 2</math> percentage points.
 | 
- Proportion of correct responses on the OCL task at Weeks -1, 2, 4, 6, and 8
 |
| Secondary Objectives   | Secondary Endpoints  |
| 
- To characterize the inter- and intra-subject variability associated with repeated high-frequency site-based computerized cognitive test administration in participants with MCI/mild AD.
 
Hypothesis: The overall standard deviation associated with the change from the placebo run-in period in average OCL repeated measurements (arcsine square root transformed) after 8 weeks of donepezil treatment is <math>\leq 0.1</math>.
  | 
- Proportion of correct responses on the OCL task
                             |

|  |  |
|--|--|
| 
- To assess the ability of a repeated high-frequency site-based computerized cognitive assessment to evaluate the potential treatment effects of donepezil after 8 weeks of treatment compared to after the placebo run-in period in participants with MCI/mild AD.
 
Hypothesis: After 8 weeks of daily treatment in participants receiving donepezil, the proportion of correct responses in the OCL task will improve relative to performance during the placebo run-in period by a clinically-meaningful (>2 percentage points) degree of change.
 | 
- Proportion of correct responses on the OCL task
 |
|--|--|

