## 3 HYPOTHESES, OBJECTIVES, AND ENDPOINTS

The following objectives will be evaluated in participants diagnosed with mild cognitive impairment or mild Alzheimer's Disease.

| Objectives   | Endpoints   |
|--|---|
| Primary  |   |
| 

To assess the ability of a repeated high-frequency site-based computerized cognitive assessment to evaluate the potential treatment effects of donepezil compared with placebo in participants with MCI/mild AD following a limited treatment duration (8 weeks treatment).

 
Hypothesis: After 8 weeks of daily treatment, the change from the placebo run-in period (Week -1) in average proportion of correct responses on the One Card Learning (OCL) task (a task of visual learning) in participants receiving donepezil compared with participants receiving placebo will be <math>\geq 2</math> percentage points.
 | 

Proportion of correct responses on the OCL task at Weeks -1, 2, 4, 6, and 8

 |

| Objectives   | Endpoints   |
|--|---|
| Secondary  |   |
| 
 
To characterize the inter- and intra-subject variability associated with repeated high-frequency site-based computerized cognitive test administration in participants with MCI/mild AD.
 
 
Hypothesis: The overall standard deviation associated with the change from the placebo run-in period in average OCL repeated measurements (arcsine square root transformed) after 8 weeks of donepezil treatment is <math>\leq 0.1</math>.
  | 
 
Proportion of correct responses on the OCL task
 
 |
| 
 
To assess the ability of a repeated high-frequency site-based computerized cognitive assessment to evaluate the potential treatment effects of donepezil after 8 weeks of treatment compared to after the placebo run-in period in participants with MCI/mild AD.
 
 
Hypothesis: After 8 weeks of daily treatment in participants receiving donepezil, the proportion of correct responses in the OCL task will improve relative to performance during the placebo run-in period by a clinically-meaningful (>2 percentage points) degree of change.
 | 
 
Proportion of correct responses on the OCL task
 
 |

| Objectives   | Endpoints  |
|--|--|
| Tertiary/Exploratory   |  |

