## 9.3 Hypotheses/Estimation

Primary:

After 8 weeks of daily treatment, the change from placebo run-in period (Week -1) in average proportion of correct responses in the One Card Learning (OCL) task (a task of visual learning) in participants receiving donepezil compared with participants receiving placebo will be  $\geq 2$  percentage points.

Secondary:

- The overall standard deviation associated with the change from placebo run-in period in average OCL repeated measurements (arcsine square root transformed) after 8 weeks of donepezil treatment is  $\leq 0.1$ .
- After 8 weeks of daily treatment in subjects receiving donepezil, the proportion of correct responses in the OCL task will improve relative to performance on the placebo run-in period by a clinically meaningful (>2 percentage points) degree of change.

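### The secondary SD hypothesis (at most 0.1) is stated for donepezil, but Section 9.6, read plainly, tests one SD common to both arms

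*Combined protocol and SAP*

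**What the plan says.** The hypothesis names the drug. Section 1.1 begins it with "The overall standard deviation associated with the change from the placebo run-in period in average OCL repeated measurements", and Section 9.3 places the change "in average OCL repeated measurements (arcsine square root transformed) after 8 weeks of donepezil treatment". Section 3 has the same statement. The limit is 0.1. The objective above it in Section 3 names no arm: "To characterize the inter- and intra-subject variability associated with repeated high-frequency site-based computerized cognitive test administration in participants with MCI/mild AD".

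The method is in Section 9.6: "The variance/covariance matrix of the average transformed OCL measurements will be estimated using a linear mixed effects model containing fixed effects" for week, treatment and week by treatment. A single unstructured covariance is estimated. The posterior is drawn from an inverse Wishart "with the model based degrees of freedom and matrix S, where S is the model-based degrees of freedom times the model estimated variance/covariance matrix". One SD is then taken from each draw: "For each generated true variance/covariance matrix, a plausible true SD of the change from baseline in average OCL measurements at Week 8". The comparison point for that change is the run-in. The hypothesis is met if the posterior probability of an SD of at most 0.1 exceeds 70%. None of these steps names an arm, a subset or a grouping of the covariance.

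Elsewhere in Section 9.6 the variance step does name the arm: both groups for the primary analysis, and the donepezil group for the other secondary hypothesis. Section 9.9 plans unequal SDs on the proportion scale. For donepezil: "In the donepezil group, the SD of the change from placebo run-in is 0.07". For placebo: "true mean change from placebo run-in period is assumed to be zero with SD of 0.06".

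**The concern.** A treatment fixed effect and its interaction with week let the means differ by arm. They do not let the variances differ. Followed as written, the rule computes a within-arm SD averaged over 24 donepezil and 12 placebo participants, and uses it to accept or reject a statement about donepezil. The sponsor's own planning figures do not treat the two SDs as equal.

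The 70% rule decides a stated secondary hypothesis about the precision of the testing platform, and precision is a large part of what this study is for. If the hypothesis and the rule refer to different quantities, a pass or a fail has no settled meaning, and the argument over which SD was meant could arise after the data are known.

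**Working it through.** **Inputs.** From Section 9.9: 24 and 12 participants, with SDs of 0.07 and 0.06 on the proportion scale. From Sections 9.3 and 9.6: limit 0.1 on the arcsine square root scale, and a posterior cut-off of 70%. Assumed, because the documents do not give them: complete data, df of 23 (donepezil only) or 34 (common), a 5 × 5 matrix for Weeks -1, 2, 4, 6 and 8, and mean accuracy p of 50% to 80% correct.

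**The plan's own power figure.** The plan gives no power for the SD hypothesis. Its only power figures are for the primary. With SE = √(0.07²/24 + 0.06²/12) = 0.02245 and power = Φ((δ − 0.02)/SE − z₀.₅₅), a true change of 3 points gives 0.625 (Table 10: 0.635) and 4 points gives 0.778 (Table 10: 0.778). All 15 cells agree within 2 points, so the SDs and arm sizes are read correctly.

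**Common SD.** √((23 × 0.07² + 11 × 0.06²)/34) = 0.0669, which is 0.956 of the donepezil SD. At that ratio the common SD equals 0.1 when the donepezil SD is 0.1/0.956 = 0.105.

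**Passing limit on the observed SD.** The rule is met when s < 0.1 × √(χ²₀.₃₀(m)/df). For a contrast taken from a 5 × 5 inverse Wishart, m = df − 4. For a direct draw of the variance of the change, used as a sensitivity check, m = df.

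| Draw | Common SD (df 34) | Donepezil only (df 23) |
|---|---|---|
| Inverse Wishart | 0.0866 | 0.0817 |
| Direct | 0.0927 | 0.0909 |

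**Example.** Observed SDs of 0.085 (donepezil) and 0.073 (placebo, planned ratio) give a common SD of 0.0813. Under the inverse Wishart the posterior probability is 84% for the common SD (met) and 62% for donepezil only (not met).

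**Pass rates at the planned SDs.** The arcsine SD is taken as SD/(2√(p(1−p))). Sample variances were simulated as SD² × χ²/df in each arm, with at least 1,000,000 trials per scenario. Both readings use the same draw. Each rate column shows common SD vs donepezil only.

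| p | Arcsine SDs (donepezil / placebo) | Inverse Wishart | Verdicts differ | Direct draw | Verdicts differ |
|---|---|---|---|---|---|
| 50% | 0.070 / 0.060 | 99% vs 89% | 11% | 99.9% vs 98% | 2% |
| 70% | 0.076 / 0.065 | 94% vs 71% | 23% | 99% vs 91% | 8% |
| 80% | 0.0875 / 0.075 | 64% vs 36% | 30% | 83% vs 64% | 21% |

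**Where the gap comes from (inverse Wishart).** Giving both arms the donepezil SD removes the mixing but keeps df 34. At 70% correct, 94% falls to 88%; dropping to df 23 then gives 71%. At 80% correct the steps are 64%, 50% and 36%.

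**Other cases.**
- Donepezil SD exactly at 0.10, placebo at the planned ratio (0.0857): 24% vs 12% (inverse Wishart), 44% vs 30% (direct).
- Placebo clearly more variable (0.08 donepezil, 0.10 placebo), inverse Wishart: 52% vs 60%, so the direction reverses.
- Planned SDs swapped between arms, 70% correct, inverse Wishart: 98% vs 96%, so no reversal.
- Fewer df (28 vs 18), 70% correct: 90% vs 58% (inverse Wishart), 98% vs 87% (direct).
- Matrix for Weeks -1 and 8 only (m = df − 1), 70% correct: 98% vs 88%.

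**The case against.** The best defence is that Section 9.6 is not ambiguous by itself: one model, one matrix, one SD, one cut-off. Two programmers would compute the same thing. The hypothesis speaks of an overall SD, the objective above it names no arm, and a shared within-arm covariance is an ordinary mixed-model choice once the arm means are fitted. The primary model also has a single unstructured matrix, so naming an arm in its variance step does not prove that an arm-specific covariance was planned. And most of the gap in pass rates reflects lost precision: with equal true SDs in both arms at 70% correct, the rates are still 88% vs 71% and verdicts differ in 20% of trials.

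Much of this stands. The common-SD reading is open, and the split above confirms that lost df is the larger part at 70% correct. The extra df is better described as power than as leniency: with both true SDs at 0.10 the rates are 30% vs 30% (direct) and 15% vs 12% (inverse Wishart). At 90% correct both readings usually fail (3% vs 2% inverse Wishart, 9% vs 7% direct), so the choice matters little there.

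The defence does not remove the mismatch. All three statements of the hypothesis tie the SD to donepezil treatment, and the word overall is undefined. A clear rule for a different quantity is still a rule for a different quantity. If a by-arm covariance was intended, Section 9.6 does not say so.

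**Conclusion.** The concern holds. As written, the decision rule does not test the hypothesis as stated. The mismatch is in the text and needs no calculation; the simulations only show its size.

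Under the prespecified inverse Wishart method and the planned SDs, verdicts differ in 11% to 30% of trials for accuracy between 50% and 80% correct, and the common-SD rule passes more often. Under a direct draw the range is 2% to 21%. These figures rest on the assumed accuracy, df, matrix size and complete data, and the direction reverses if placebo is clearly the more variable arm. The primary analysis and Table 10 are unaffected. The plan should be corrected, but the trial's main conclusion does not depend on it.

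**What to change.** Before unblinding, choose one of two changes.

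1. State in Section 9.6 that the 70% rule applies to the donepezil-arm SD. Take the covariance from that arm, either by fitting the model to it or by grouping the covariance by treatment. Use that arm's own df, keep the inverse Wishart method, and report the common SD as supportive. This follows the wording of the three hypothesis statements.
2. If a common SD is intended, leave Section 9.6 as it is and reword the hypothesis in Sections 1.1, 3 and 9.3 so that it no longer refers to donepezil treatment alone.

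The first costs one sentence and a small code change. It also estimates a 5 × 5 matrix from about 24 people, with about 23 df in place of 34, so the posterior is wider and the chance of passing at the planned SDs falls (from 94% to 71% at an assumed 70% correct). The second costs only the rewording.
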